2.2 SAFETY OBJECTIVE

The safety objective for this study is to evaluate the safety of ^{129}Xe MRI procedures and of AZM+SOC compared with SOC on the basis of the following endpoints:

- Incidence and severity of adverse events, with severity determined according to the World Health Organization (WHO) toxicity scale
- Change from baseline in targeted vital signs
- Change from baseline in targeted clinical laboratory test results
- Change from baseline in ECG data

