4.5.5 Hearing Assessment

Patients in Cohort A will complete the *HHIE-S* ([Appendix 7](#)) and be queried on any onset hearing loss, worsening hearing loss, or hearing disturbances at specified timepoints.

Any patient in Cohort A randomized to azithromycin reporting onset or worsening hearing loss, reporting hearing disturbances, or demonstrating any decline in the interpretation of the HHIE-S score during the study will permanently discontinue azithromycin and be referred for formal audiology testing. Any patient who permanently discontinues azithromycin should be asked to continue all other study assessments, with the exception of azithromycin administration, through the end of the study.

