5.1.2.7 Tinnitus or Hearing Loss

Hearing disturbances including hearing loss, deafness and/or tinnitus, and reports of taste/smell perversion and/or loss have been reported in postmarketing surveillance and in randomized controlled trials assessing benefit/risk profile of azithromycin to prevent AEx in COPD (Albert et al. 2011).

Patients in Cohort A will complete the *HHIE-S* (see [Appendix 7](#)) to assess perceived hearing disability. Those with *known significant hearing impairment at screening will be excluded*. Patients who are randomized to the azithromycin arm complaining of worsening tinnitus, *onset hearing loss*, or worsening hearing loss *will permanently discontinue azithromycin and be referred for formal audiology testing*.

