5.3.2 Eliciting Adverse Event Information

A consistent methodology of non-directive questioning should be adopted for eliciting adverse event information at all patient evaluation timepoints. Examples of non-directive questions include the following:

"How have you felt since your last clinic visit?"

"Have you had any new or changed health problems since you were last here?"

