6.5 SAFETY ANALYSES

The safety analysis population will consist of all patients who received at least one dose of study drug during the 48-week open-label treatment period, with patients grouped according to treatment received (AZM + SOC or SOC).

Safety will be assessed through summaries of exposure to study treatment, adverse events, changes in laboratory test results, and changes in vital signs and ECGs (see Section [2.2](#)).

Study treatment exposure (such as treatment duration, total dose received, and number of cycles and dose modifications) will be summarized with descriptive statistics.

All verbatim adverse event terms will be mapped to Medical Dictionary for Regulatory Activities (MedDRA) thesaurus terms, and adverse event severity will be graded according to the WHO toxicity grading scale. All adverse events, serious adverse events, adverse events leading to death, adverse events of special interest, and adverse events leading to study treatment discontinuation that occur on or after the first dose of study treatment (i.e., treatment emergent adverse events) will be summarized by mapped term, appropriate thesaurus level, and severity grade. For events of varying severity, the highest grade will be used in the summaries. Deaths and cause of death will be summarized.

Relevant laboratory, vital sign (pulse rate, respiratory rate, blood pressure, pulse oximetry, and temperature), and ECG data will be displayed by time, with grades identified where appropriate. Additionally, a shift table of selected laboratory tests will be used to summarize the baseline and maximum postbaseline severity grade. Changes in vital signs and ECGs will be summarized.

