6.6 EXPLORATORY ANALYSIS OF PATIENT-REPORTED OUTCOME MEASURES

The PRO measures for this study are as follows:

- SCRQ-C change from baseline to Week 24 and Week 48
- Change in cough and sputum as measured by visual analogue score for dyspnea, cough sputum production (100 mm) from baseline to Week 24 and Week 48

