^{bb} All adverse events, including serious adverse events and adverse events of special interest. *Patients in Cohort A randomized to azithromycin will additionally be queried on any onset or worsening hearing loss or hearing disturbances.*

^{cc} 3-month drug supply limited to Cohort A. Completion of all Visit 2 baseline assessments required to be completed prior to dispensing first dose of azithromycin.

^{dd} Patients will be instructed to complete a diary that will be reviewed at study visits.

Appendix 2

St. George's Respiratory Questionnaire for COPD Patients

ST. GEORGE'S RESPIRATORY QUESTIONNAIRE for COPD patients

(SGRQ-C)

*This questionnaire is designed to help us learn much more about how your breathing is troubling you and how it affects your life.
We are using it to find out which aspects of your illness cause you most problems, rather than what the doctors and nurses think your problems are.*

Please read the instructions carefully and ask if you do not understand anything. Do not spend too long deciding about your answers.

ID: _____

Date: _____ / _____ / _____ (dd/mm/yy)

Before completing the rest of the questionnaire:

Please select one box to show how you describe your current health:

Very good

Good

Fair

Poor

Very poor

Version: 1st Sept 2005

Copyright reserved
[name], PhD FRCP
Professor of Respiratory Medicine,
St. George's University of London,
[name]
[name].

[contact]
[contact]

UK/ English version COPD

1/7
continued...

SGRQ-C - United Kingdom/English
SGRQ-C_AU1.0_eng-QBer1.doc

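### Appendix 1 footnote bb directs the hearing query to azithromycin patients while Section 4.5.5 directs it to all of Cohort A, so hearing adverse events may be prompted unequally between arms (minor)

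*Combined protocol and SAP*

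**What the plan says.** Sections 1.3, 3.3.2 and 5.1.2.7 name impaired hearing as a risk of long-term azithromycin, and Section 2.2 sets out to compare the safety of AZM + SOC with SOC.

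**Collection.** Under Section 4.5.5, Cohort A patients complete the HHIE-S "and be queried on any onset hearing loss, worsening hearing loss, or hearing disturbances at specified timepoints". Section 5.1.2.7 gives the purpose of the HHIE-S: "to assess perceived hearing disability". The Appendix 1 row schedules it at screening and Weeks 12, 24 and 48, and footnote l limits it by cohort, not by arm. Footnote bb, attached to the adverse events row, reads: "Patients in Cohort A randomized to azithromycin will additionally be queried on any onset or worsening hearing loss or hearing disturbances". No other instruction in the schedule covers the hearing query.

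**General questioning.** Section 5.3.2 sets the default: "A consistent methodology of non-directive questioning should be adopted for eliciting adverse event information at all patient evaluation timepoints". Section 4.5.13 also has the investigator ask directed questions about adverse events at visits, with no restriction by arm and no mention of hearing.

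**Analysis.** Section 2.2 lists adverse events, vital signs, ECG data and "Change from baseline in targeted clinical laboratory test results". Section 6.5 lists exposure, "adverse events, changes in laboratory test results, and changes in vital signs and ECGs". Section 6.6 lists "SCRQ-C change from baseline to Week 24 and Week 48" (as printed) and a visual analogue score. The HHIE-S is in none of the three.

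**Consequences of a hearing finding.** In the azithromycin arm, a hearing complaint or a decline in HHIE-S interpretation stops azithromycin and triggers audiology referral. Such a patient "should be asked to continue all other study assessments, with the exception of azithromycin administration, through the end of the study".

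**The concern.** In an open-label trial, a specific question asked in one arm and not the other can raise the number of reports in the first arm without any difference in the underlying events. The arm that footnote bb names is the one in which hearing harm is expected. If sites follow the footnote as printed, any between-arm difference in hearing adverse events mixes a drug effect with a difference in how often patients were asked. The likely direction is against azithromycin.

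The HHIE-S is the one hearing measure timed alike in both arms. With no summary of it in 2.2, 6.5 or 6.6, the protocol offers nothing to set beside the adverse event tables as a check.

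Care of individual patients is not at issue: Section 5.5.1 requires reported events to be followed to resolution or stability.

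**Working it through.** The plan states no figure on this point, so there is nothing to reproduce. The check compares the two instructions and counts prompts from the schedule.

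**1. The two instructions.** Section 4.5.5 opens with patients in Cohort A and does not separate the arms, but leaves the timepoints to be specified elsewhere. Appendix 1 is where timepoints are set, and its only hearing-query text, footnote bb, names the azithromycin arm. A site working from the schedule therefore finds no query set for SOC patients.

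**2. Prompts at post-baseline adverse event contacts (Appendix 1, Cohort A, footnote bb read plainly).**

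| Contact | Weeks since previous contact | Azithromycin prompt | SOC prompt |
|---|---|---|---|
| Week 6 | 6 | query | none |
| Week 12 | 6 | query + HHIE-S | HHIE-S |
| Week 24 | 12 | query + HHIE-S | HHIE-S |
| Week 36 | 12 | query | none |
| Week 48 | 12 | query + HHIE-S | HHIE-S |
| Week 52 (telephone) | 4 | query | none |

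Azithromycin: 6 of 6. SOC: 3 of 6. Intervals ending at an HHIE-S contact total 6 + 12 + 12 = 30 weeks. Those ending at a contact with no SOC prompt total 6 + 12 + 4 = 22 weeks. The sum is 52.

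**3. Apparent risk ratio when the true ratio is 1.** Assumptions: events are spread evenly over 52 weeks; the HHIE-S counts as a full prompt; an unprompted contact captures a fraction u of what a prompted one captures. The documents give no value for u, so a range is shown.

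- *Every event resolves before the next HHIE-S.* An event missed at an unprompted contact is lost. Ratio = 52 / (30 + 22u).
- *Hearing loss persists to the next HHIE-S.* Onset in Weeks 0–6 is picked up at Week 12, and onset in Weeks 24–36 at Week 48. Only the 4 weeks after Week 48 have no later SOC prompt. Ratio = 52 / (48 + 4u).

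| u | Events resolve early | Events persist |
|---|---|---|
| 1.00 | 52/52 = 1.00 | 52/52 = 1.00 |
| 0.75 | 52/46.5 = 1.12 | 52/51 = 1.02 |
| 0.50 | 52/41 = 1.27 | 52/50 = 1.04 |
| 0.25 | 52/35.5 = 1.46 | 52/49 = 1.06 |

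**4. What an HHIE-S summary could show.** With 50 per arm less the plan's 10% drop-out, 45 per arm:

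- Mean change: 95% CI half-width = t(0.975, 88) × √(2/45) = 0.42 SD. The documents give no HHIE-S SD.
- Proportion with any decline: half-width = 1.96 × √(2p(1−p)/45), which is 9.0, 12.4 and 16.5 percentage points for assumed p of 0.05, 0.10 and 0.20.

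That is enough for a descriptive check and too wide to settle a small difference.

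**The case against.** **Footnote bb does not exclude SOC patients.** It says *additionally* and never says only. It could mean an extra safety question for the arm with the hearing stopping rule, with the 4.5.5 query still put to everyone. This stands as a possible reading, so unequal prompting follows from the footnote's plain reading and is not certain. The ambiguity itself still needs removing.

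**SOC patients are not left unasked.** Section 4.5.13 requires directed adverse event questions in both arms, and the limited physical examination, which includes the ears, is scheduled at Weeks 6 and 36. Neither is a hearing question, but both argue against a very low u.

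**The larger ratios need short-lived events.** A reader might take 1.12 to 1.46 as the expected distortion. The documents do not support that. Section 5.1.2 calls decreased hearing reversible but gives no time to recovery, and hearing loss that lasts until the next HHIE-S brings the range down to 1.02 to 1.06.

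**The HHIE-S may be analysed elsewhere.** A reader might infer that the scores will never be compared between arms. The separate SAP that the protocol cites is not in the supplied document, so this cannot be said. Section 6.5, unlike 6.4.1 to 6.4.3, does not refer to the SAP, but that does not show the SAP has no such table. A SAP could in any case not correct an instruction to sites.

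**The HHIE-S shares the weakness.** It is open-label self-report, and a decline stops treatment in one arm only. This stands, and it limits the summary to a supporting role.

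**Conclusion.** Section 4.5.5 and footnote bb disagree on who receives the hearing query. On a plain reading, the footnote prompts azithromycin patients at twice as many contacts as SOC patients (6 against 3). With no true difference and u between 0.75 and 0.25, the apparent hearing risk ratio is about 1.02 to 1.06 if events persist to the next HHIE-S. It reaches 1.12 to 1.46 only if every event resolves before then, and it is 1.00 if prompting has no effect. The size rests on assumed values of u, even spread of events, and the HHIE-S working as a full prompt. The count of prompts comes directly from the schedule.

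Severity is minor. The primary objective is unaffected, and hearing events are still recorded and tabulated by arm. Section 5.1 describes azithromycin's safety profile as already well characterised. The documents do not support a claim that the hearing comparison is invalid, or that SOC patients receive no questioning that could bring out a hearing problem. The absent HHIE-S summary is a secondary gap in the protocol text, which the SAP may already fill.

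**What to change.** 1. Amend footnote bb to match 4.5.5, so that both Cohort A arms receive the same directed hearing query at the same contacts. The stopping and referral rule stays specific to azithromycin. Cost: a few words, and one more question to SOC patients at contacts already scheduled.

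2. As a supportive item, add to 6.5 a descriptive by-arm summary for Cohort A of change from screening in HHIE-S score and shift in interpretation category at Weeks 12, 24 and 48. Use the grouping that 6.5 applies to the adverse event tables (treatment received) so that the two can be read together. Keep scores taken after azithromycin is stopped, since 4.5.5 asks those patients to continue assessments. State beside the table that the HHIE-S is open-label self-report with a stopping consequence in one arm only. Cost: one table and no new HHIE-S collection. The HHIE-S row has no early-termination mark, so a patient who stops azithromycin between visits is next scored at the following scheduled HHIE-S visit. If the SAP already contains this summary, a cross-reference in 6.5 is enough.

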6.6 EXPLORATORY ANALYSIS OF PATIENT-REPORTED OUTCOME MEASURES

The PRO measures for this study are as follows:

- SCRQ-C change from baseline to Week 24 and Week 48
- Change in cough and sputum as measured by visual analogue score for dyspnea, cough sputum production (100 mm) from baseline to Week 24 and Week 48

6.7 EXPLORATORY BIOMARKER ANALYSES

Although no formal statistical analysis of exploratory biomarkers will be performed, data may be analyzed in the context of this study and in aggregate with data from other studies. Exploratory biomarker objectives and endpoints are described in Section 2.3.

Pharmacodynamic (PD) biomarkers (e.g., eosinophils, neutrophils, sputum mucins, and serum CRP) may be assessed to determine pharmacological activity of azithromycin in patients with and without chronic bronchitis. Data will be summarized by absolute levels of the biomarker, as well as absolute and relative changes from levels at randomization visit, for each treatment group. Additional PD analyses will be conducted as appropriate.

Additional exploratory analyses to understand molecular pathways will evaluate the relationship at baseline and longitudinally between biomarkers in sputum, blood (serum, plasma, and RNA from blood) or other biomarker endpoints.

6.8 INTERIM ANALYSES

An interim analysis may be performed to assess for changes in VDP and/or other ¹²⁹Xe MRI metrics relative to other clinical assessments, at the Sponsor's discretion.

Given the exploratory nature of this study, the Sponsor may choose to conduct additional interim efficacy analyses. The decision to conduct an optional interim analysis and the timing of the analysis will be documented in the Sponsor's trial master file prior to the conduct of the interim analysis. The interim analysis will be performed and interpreted by the Sponsor's study team personnel.

7. DATA COLLECTION AND MANAGEMENT

7.1 DATA QUALITY ASSURANCE

eCRF and paper patient reported questionnaires including SGRQ-C and mMRC are the primary data collection instruments and are treated as source data. All source data will be entered into the EDC system by site staff.

The Sponsor will provide support for data management of this study, including quality checking of the data in the EDC. Data entered manually will be collected via EDC through use of eCRFs. Sites will be responsible for data entry into the EDC system. In the event of discrepant data, the Sponsor will request data clarification from the sites, which the sites will resolve electronically in the EDC system.

The Sponsor will produce an EDC Study Specification document that describes the quality checking to be performed on the data. Central laboratory data and other electronic data will be sent directly to the Sponsor, using the Sponsor's standard procedures to handle and process the electronic transfer of these data.

eCRFs and correction documentation will be maintained in the EDC system's audit trail. System backups for data stored by the Sponsor and records retention for the study data will be consistent with the Sponsor's standard procedures.

7.2 ELECTRONIC CASE REPORT FORMS

eCRFs are to be completed through use of a Sponsor-designated EDC system. Sites will receive training and have access to a manual for appropriate eCRF completion. eCRFs will be submitted electronically to the Sponsor and should be handled in accordance with instructions from the Sponsor.

All eCRFs should be completed by designated, trained site staff. eCRFs should be reviewed and electronically signed and dated by the investigator or a designee.

At the end of the study, the investigator will receive patient data for his or her site in a readable format that must be kept with the study records. Acknowledgement of receipt of the data is required.

7.3 SOURCE DATA DOCUMENTATION

Study monitors will perform ongoing source data verification and review to confirm that critical protocol data (i.e., source data) entered into the eCRFs by authorized site personnel are accurate, complete, and verifiable from source documents.

Source documents (paper or electronic) are those in which patient data are recorded and documented for the first time. They include, but are not limited to, hospital records, clinical and office charts, laboratory notes, memoranda, patient-reported outcomes, evaluation checklists, pharmacy dispensing records, recorded data from automated instruments, copies of transcriptions that are certified after verification as being accurate and complete, microfiche, photographic negatives, microfilm or magnetic media, X-rays, patient files, and records kept at pharmacies, laboratories, and medico-technical departments involved in a clinical trial.

Before study initiation, the types of source documents that are to be generated will be clearly defined in the Trial Monitoring Plan. This includes any protocol data to be entered directly into the eCRFs (i.e., no prior written or electronic record of the data) and considered source data.

Source documents that are required to verify the validity and completeness of data entered into the eCRFs must not be obliterated or destroyed and must be retained per the policy for retention of records described in Section [7.5](#).

To facilitate source data verification and review, the investigators and institutions must provide the Sponsor direct access to applicable source documents and reports for trial-related monitoring, Sponsor audits, and IRB/EC review. The study site must also allow inspection by applicable health authorities.

7.4 USE OF COMPUTERIZED SYSTEMS

When clinical observations are entered directly into a study site's computerized medical record system (i.e., in lieu of original hardcopy records), the electronic record can serve as the source document if the system has been validated in accordance with health authority requirements pertaining to computerized systems used in clinical research. An acceptable computerized data collection system allows preservation of the original entry of data. If original data are modified, the system should maintain a viewable audit trail that shows the original data as well as the reason for the change, name of the person making the change, and date of the change.

7.5 RETENTION OF RECORDS

Records and documents pertaining to the conduct of this study and the distribution of IMP, including eCRFs, electronic or paper PRO data (if applicable), Informed Consent Forms, laboratory test results, and medication inventory records, must be retained by the Principal Investigator for 15 years after completion or discontinuation of the study or for

the length of time required by relevant national or local health authorities, whichever is longer. After that period of time, the documents may be destroyed, subject to local regulations.

No records may be disposed of without the written approval of the Sponsor. Written notification should be provided to the Sponsor prior to transferring any records to another party or moving them to another location.

Roche will retain study data for 25 years after the final study results have been reported or for the length of time required by relevant national or local health authorities, whichever is longer.

8. ETHICAL CONSIDERATIONS

8.1 COMPLIANCE WITH LAWS AND REGULATIONS

This study will be conducted in full conformance with the ICH E6 guideline for Good Clinical Practice and the principles of the Declaration of Helsinki, or the applicable laws and regulations of the country in which the research is conducted, whichever affords the greater protection to the individual. The study will comply with the requirements of the ICH E2A guideline (Clinical Safety Data Management: Definitions and Standards for Expedited Reporting). Studies conducted in the United States or under a U.S. Investigational New Drug (IND) Application will comply with U.S. FDA regulations and applicable local, state, and federal laws. Studies conducted in the European Union or European Economic Area will comply with the E.U. Clinical Trial Directive (2001/20/EC) and applicable local, regional, and national laws.

8.2 INFORMED CONSENT

The Sponsor's sample Informed Consent Form (and ancillary sample Informed Consent Forms such as an Assent Form or Mobile Nursing Informed Consent Form, if applicable) will be provided to each site. If applicable, it will be provided in a certified translation of the local language. The Sponsor or its designee must review and approve any proposed deviations from the Sponsor's sample Informed Consent Forms or any alternate consent forms proposed by the site (collectively, the "Consent Forms") before IRB/EC submission. The final IRB/EC-approved Consent Forms must be provided to the Sponsor for health authority submission purposes according to local requirements.

If applicable, the Informed Consent Form will contain separate sections for any optional procedures. The investigator or authorized designee will explain to each patient the objectives, methods, and potential risks associated with each optional procedure. Patients will be told that they are free to refuse to participate and may withdraw their consent at any time for any reason. A separate, specific signature will be required to document a patient's agreement to participate in optional procedures. Patients who decline to participate will not provide a separate signature.

The Consent Forms must be signed and dated by the patient or the patient's legally authorized representative before his or her participation in the study. The case history or clinical records for each patient shall document the informed consent process and that written informed consent was obtained prior to participation in the study.

The Consent Forms should be revised whenever there are changes to study procedures or when new information becomes available that may affect the willingness of the patient to participate. The final revised IRB/EC-approved Consent Forms must be provided to the Sponsor for health authority submission purposes.

If the Consent Forms are revised (through an amendment or an addendum) while a patient is participating in the study, the patient or a legally authorized representative must re-consent by signing the most current version of the Consent Forms or the addendum, in accordance with applicable laws and IRB/EC policy. For any updated or revised Consent Forms, the case history or clinical records for each patient shall document the informed consent process and that written informed consent was obtained using the updated/revised Consent Forms for continued participation in the study.

A copy of each signed Consent Form must be provided to the patient or the patient's legally authorized representative. All signed and dated Consent Forms must remain in each patient's study file or in the site file and must be available for verification by study monitors at any time.

For sites in the United States, each Consent Form may also include patient authorization to allow use and disclosure of personal health information in compliance with the U.S. Health Insurance Portability and Accountability Act (HIPAA) of 1996. If the site utilizes a separate Authorization Form for patient authorization for use and disclosure of personal health information under the HIPAA regulations, the review, approval, and other processes outlined above apply except that IRB review and approval may not be required per study site policies.

